9.3.2. Columbia Suicide Severity Rating Scale (C-SSRS)

The C-SSRS will be analyzed and listed. The frequency and percentage of subjects with each response for suicidal ideation, intensity of ideation, and suicidal behavior items will be summarized for the treatment period (Weeks 24-since last visit, Week 48-since last visit, Week 72-since last visit and Week 96-since last visit) in MT-1186-A03. The distribution of responses for most severe suicidal ideation and suicidal behavior will also be presented for the treatment period.

1. The counting method of suicidal ideation:

In the treatment period, the subject who has at least one of each suicidal ideation 5 items will be counted once. In case subjects will report suicidal ideation several times within this period, then the subject will be counted in the most severe suicidal ideation item.

2. The counting method of suicidal behavior:

In the treatment period, the subject who has at least one of each suicidal behavior 5 items and non-suicidal self-injurious behavior item will be counted once. In case subjects will report suicidal behavior with non-suicidal self-injurious behavior several times within this period, then the subject will be counted in the most severe suicidal behavior item.

3. The counting method of suicidal ideation or suicidal behavior

In the treatment period, the subjects who meets the criteria of (1) or (2) will be counted.

4. The counting method of non-suicidal self-injurious behavior item

In the treatment period the subjects who has non-suicidal self-injurious behavior item will be counted.

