### **9.4 Exclusion Criteria**

Subjects who meet any of the following criteria will be excluded from the study:

1. Subjects who are able to bear children and who do not have a negative pregnancy test, women who are nursing or who do not agree to use a highly effective form of contraception from Visit 1 until 3 months after the last dose of study medication. Refer to Appendix 2 for additional contraceptive information.
2. Subjects who have a significant risk of suicide. Subjects with any suicidal behavior or suicidal ideation of type 4 (active suicidal ideation with some intent to act, without a specific plan) or type 5 (active suicidal ideation with specific plan and intent) based on the C-SSRS at Visit 1.
3. Subjects who are not eligible to continue in the study, as judged by the Investigator.
4. Subjects who are unable to take their medications orally or through a PEG/RIG tube.

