**C-SSRS**

For the C-SSRS, the number and percentage of subjects with suicidal ideation or suicidal behavior as recorded on the C-SSRS scale will be presented. The distribution of responses for most severe suicidal ideation and suicidal behavior during the lifetime history and the treatment period will be presented.

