8. DATA CONVENTIONS

8.1. Baseline Definition

In general, the data at Week 48 in Study MT-1186-A01 (same time as A03 Visit 1/Day 1) will be used as the baseline for statistical analysis in this study. The analyses involving calculation of change from baseline will be based on the absolute changes from baseline (not percentage), unless stated otherwise.

The time (days) to death, tracheostomy, or permanent assisted mechanical ventilation (≥ 23 hours/day) will be analyzed using the time from first study drug administration in the MT-1186-A01 study.

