8.4.3.2. Columbia Suicide Severity Rating Scale (C-SSRS)

The C-SSRS is a clinician-rated instrument that captures the occurrence, severity, and frequency of suicide-related ideations and behaviours during the assessment period. Suicidal ideation is classified on a 5-item scale: 1 (wish to be dead), 2 (nonspecific active suicidal thoughts), 3 (active suicidal ideation with any methods [not plan] without intent to act), 4 (active suicidal ideation with some intent to act, without specific plan), and 5 (active suicidal ideation with specific plan and intent). The C-SSRS also captures information about the intensity of ideation, specifically the frequency, duration, controllability, deterrents, and reasons for the most severe types of ideation. Suicidal behavior is classified on a 5-item scale: 0 (no suicidal behavior), 1 (preparatory acts or behavior), 2 (aborted attempt), 3 (interrupted attempt), and 4 (actual attempt). More than 1 classification can be selected provided they represent separate episodes. For actual attempts only, the actual or potential lethality is classified for the initial, most lethal, and most recent attempts. C-SSRS will be evaluated at Day 1, Week 24, Week 48, Week 72 and Week 96.

The severe level of suicidal ideation 5 items from low to high:

- 1: Wish to be dead
- 2: Non-specific active suicidal thoughts
- 3: Active suicidal ideation with any methods (not plan) without intent to act
- 4: Active suicidal ideation with some intent to act, without specific plan
- 5: Active suicidal ideation with specific plan and intent

The severe level of suicidal behavior 5 items from low to high:

- 1: Preparatory Acts or Behavior
- 2: Aborted Attempt
- 3: Interrupted Attempt
- 4: Actual Attempt
- 5: Suicidal Behavior

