10.3. Analysis Visits to Report

Efficacy:

| Analysis Visit | Apply to |
|----------------|--------------|
| Baseline | All efficacy |
| Week 24 | All efficacy |
| Week 48 | All efficacy |
| Week 72 | All efficacy |
| Week 96 | All efficacy |

Statistical Analysis Plan
Protocol No. MT-1186-A03

Mitsubishi Tanabe Pharma America, Inc.

Safety:

| Analysis Visit | Apply to | | | |
|----------------|------------------|-------------|--------------|--------|
| | Laboratory Tests | Vital Signs | 12-Lead ECGs | C-SSRS |
| Baseline | X | X | X | X |
| Week 12 | | X | | |
| Week 24 | X | X | | X |
| Week 48 | X | X | X | X |
| Week 72 | X | X | | X |
| Week 96 | X | X | X | X |

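### For C-SSRS ideation types 1 to 3, the planned summaries cannot separate ideation persisting from Day 1 from ideation that is new or worsened since Day 1

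*SAP*

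**What the plan says.** C-SSRS is one of the primary safety endpoints (Protocol 7.2.1, SAP 3.2.1).

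- **Entry.** Exclusion criterion 2 in Protocol 9.4 covers "Subjects with any suicidal behavior or suicidal ideation of type 4 (active suicidal ideation with some intent to act, without a specific plan", and then type 5, as rated at Visit 1. Types 1 to 3 are not named.
- **Collection and baseline.** SAP 8.4.3.2: "C-SSRS will be evaluated at Day 1, Week 24, Week 48, Week 72 and Week 96". SAP 8.1: "In general, the data at Week 48 in Study MT-1186-A01 (same time as A03 Visit 1/Day 1) will be used as the baseline".
- **Counting.** SAP 9.3.2 summarizes the since-last-visit records at Weeks 24, 48, 72 and 96. For ideation: "In the treatment period, the subject who has at least one of each suicidal ideation 5 items will be counted once". For repeated reports: "In case subjects will report suicidal ideation several times within this period, then the subject will be counted in the most severe suicidal ideation item". Then: "The distribution of responses for most severe suicidal ideation and suicidal behavior will also be presented for the treatment period".
- **Visits to report.** The safety table in SAP 10.3 has the row "Baseline | X | X | X | X", whose last column is C-SSRS. Baseline is therefore a reported visit there, although 9.3.2 does not mention it.
- **Protocol counterpart.** Protocol 17.3.5.4: "The distribution of responses for most severe suicidal ideation and suicidal behavior during the lifetime history and the treatment period will be presented". The SAP keeps only the treatment period. SAP Section 11 lists a single change from the protocol, and it concerns physical examinations.

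**The concern.** The study has one arm and no hypothesis test (Protocol 14.5, SAP 7.2), so each subject's own Day 1 record is the only comparator inside it. Under the SAP rules, a subject with type 2 at Day 1 and again at Week 24 falls in the same cell as a subject with no ideation at Day 1 and type 2 at Week 24. The first has not changed and the second is a new case.

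The same SAP already uses a per-subject baseline reference elsewhere. SAP 9.3.3 tabulates shifts from no potentially clinically significant laboratory value at baseline to one after baseline, and the TEAE definition in SAP 8.4.3.1 distinguishes new events from events that increased in severity. Protocol 17.3.1 also foresees changes from baseline for primary endpoints where applicable. At stake is how a descriptive safety result is read. No error rate or sample size is involved.

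**Working it through.** The plan states no figure for this item, so there is nothing to reproduce. The check is to set the entry rule against the counting rule.

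**Step 1: possible Day 1 states.** By Protocol 9.4, an enrolled subject has no ideation or ideation of type 1, 2 or 3 at Day 1, and no suicidal behavior. SAP 8.4.1.1 says the data review confirmed that no inclusion or exclusion deviation occurred.

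**Step 2: cross these with the worst on-study type.** The planned distribution gives one total per row and does not split it by column.

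| Worst on-study type | Day 1: none | Day 1: type 1 | Day 1: type 2 | Day 1: type 3 |
|---|---|---|---|---|
| 1 | new | unchanged | lower | lower |
| 2 | new | worse | unchanged | lower |
| 3 | new | worse | worse | unchanged |
| 4 | new | worse | worse | worse |
| 5 | new | worse | worse | worse |

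In rows 1 to 3, 6 of the 12 combinations are new or worse (1 + 2 + 3) and 6 are unchanged or lower (3 + 2 + 1). A row total cannot tell these apart. In rows 4 and 5, all 8 combinations are new or worse. On-study suicidal behavior is likewise new relative to Day 1.

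**Step 3: size.** The documents give no prevalence of type 1 to 3 ideation at Day 1. The following is illustration only. Take N = 140 (the approximate enrollment in SAP 4.2) and three assumed quantities: p0, the share with type 1 to 3 ideation at Day 1; s, the share of those who report ideation again on study; and q, the rate of new ideation among the rest.

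Counted = N × p0 × s + N × (1 − p0) × q

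| p0 | s | q | Reporting again | New | Counted | Share with Day 1 ideation |
|---|---|---|---|---|---|---|
| 2% | 50% | 2% | 1.4 | 2.7 | 4.1 (3.0%) | 34% |
| 2% | 50% | 5% | 1.4 | 6.9 | 8.3 (5.9%) | 17% |
| 10% | 50% | 2% | 7.0 | 2.5 | 9.5 (6.8%) | 74% |
| 15% | 80% | 2% | 16.8 | 2.4 | 19.2 (13.7%) | 88% |
| 15% | 80% | 5% | 16.8 | 6.0 | 22.8 (about 16%) | 74% |

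Third row in full: 140 × 0.10 × 0.50 = 7.0; 140 × 0.90 × 0.02 = 2.5; 7.0 / 9.5 = 74%. The reporting-again column includes any subjects who worsened. Over p0 of 2 to 15%, s of 50 to 80% and q of 2 to 5%, the share of counted subjects who already had ideation at Day 1 runs from 17% to 88%. A range that wide shows that the size cannot be inferred from the documents.

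**The case against.** The strongest reply is that the information is not lost. SAP 10.3 reports C-SSRS at Baseline, SAP 9.3.2 lists the data, and SAP 7.1 sorts listings by subject and, where applicable, visit. With about 140 subjects, a reader could trace each positive case back to Day 1. That stands: what is missing is a summary, not data. But a group-level Baseline column does not link a subject's Day 1 category to later ones, and listings leave the classification to the reader with no rule fixed in advance.

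Three further points also stand.

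- The investigator may exclude a subject under criterion 3 of Protocol 9.4. That is discretionary and does not bar types 1 to 3.
- C-SSRS is not singled out. The investigator's ECG assessment and orthostatic hypotension are also tabulated by visit without a shift (SAP 9.3.4 and 9.3.5).
- A lifetime summary would not separate persisting from new ideation, and SAP Section 2 lets the SAP supersede the protocol's statistical text. The lifetime omission is therefore a documentation point.

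A reader might infer that the tables cannot show at all whether suicidality arose or worsened. The documents do not support that: types 4 and 5 and suicidal behavior are barred at entry, so any on-study occurrence is already new or worse. A reader might also infer that ideation present at Day 1 is unrelated to treatment and should be set aside. That fails too, because Day 1 is Week 48 of MT-1186-A01, after treatment in the parent study, and such ideation may have started there.

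**Conclusion.** The point holds for ideation types 1 to 3. For these, the planned summaries mix unchanged or lower ideation with ideation that is new or worsened since A03 Day 1. It does not hold for types 4 and 5 or for suicidal behavior. That limit rests on the entry criterion and on the SAP's statement that no eligibility deviation occurred.

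The size is unknown. Any specific inflation of the reported rate would be assumption, since neither the Day 1 prevalence nor its persistence is given. The consequence is confined to interpreting a descriptive primary safety endpoint. This is a minor improvement worth making because it costs almost nothing.

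Two smaller discrepancies go with it: SAP 9.3.2 covers Weeks 24 to 96 while 10.3 includes Baseline, and the protocol's lifetime-history distribution was dropped without an entry in SAP Section 11.

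**What to change.** 1. Add to SAP 9.3.2 a per-subject shift table from the Day 1 (A01 Week 48) C-SSRS category to the worst post-baseline category.
2. Add counts of subjects with new ideation or behavior (none at Day 1) and of subjects with worsening (a higher category than at Day 1). Label both as since A03 Day 1. Use subjects with both a baseline and a post-baseline assessment as the denominator.
3. Present these alongside the planned all-subject counts, not in place of them, so that ideation which began during A01 stays visible.
4. Reconcile SAP 9.3.2 with 10.3 by stating how Baseline will be shown for C-SSRS.
5. Restore the lifetime-history distribution from Protocol 17.3.5.4, or record its removal and the reason in SAP Section 11.

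The shift table and counts use assessments already scheduled at Day 1 and Weeks 24, 48, 72 and 96, so no new data collection is needed. The downside is one extra descriptive table.

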Has subject engaged in Non-Suicidal Self-Injurious Behavior? Interrupted Attempt: When the person is interrupted (by an outside circumstance) from starting the potentially self-injurious act (if not for that, actual attempt would have occurred). Overdose: Person has pills in hand but is stopped from ingesting. Once they ingest any pills, this becomes an attempt rather than an interrupted attempt. Shooting: Person has gun pointed toward self, gun is taken away by someone else, or is somehow prevented from pulling trigger. Once they pull the trigger, even if the gun fails to fire, it is an attempt. Jumping: Person is poised to jump, is grabbed and taken down from ledge. Hanging: Person has noose around neck but has not yet started to hang - is stopped from doing so. Has there been a time when you started to do something to end your life but someone or something stopped you before you actually did anything? If yes, describe: _____		Yes  No   Total # of interrupted _____
Aborted Attempt: When person begins to take steps toward making a suicide attempt, but stops themselves before they actually have engaged in any self-destructive behavior. Examples are similar to interrupted attempts, except that the individual stops him/herself, instead of being stopped by something else. Has there been a time when you started to do something to try to end your life but you stopped yourself before you actually did anything? If yes, describe: _____		Yes  No   Total # of aborted _____
Preparatory Acts or Behavior: Acts or preparation towards imminently making a suicide attempt. This can include anything beyond a verbalization or thought, such as assembling a specific method (e.g., buying pills, purchasing a gun) or preparing for one's death by suicide (e.g., giving things away, writing a suicide note). Have you taken any steps towards making a suicide attempt or preparing to kill yourself (such as collecting pills, getting a gun, giving valuables away or writing a suicide note)? If yes, describe: _____		Yes  No   
Suicidal Behavior: Suicidal behavior was present during the assessment period?		Yes  No   
Suicide:		Yes  No   

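### The C-SSRS counting rule in SAP 9.3.2, on its most natural reading, counts non-suicidal self-injury as suicidal behavior and so can inflate the behavior and combined rates

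*SAP*

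**What the plan says.** SAP 9.3.2 gives four counting rules for the treatment period.

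- **Rule 1, ideation:** "the subject who has at least one of each suicidal ideation 5 items will be counted once".
- **Rule 2, suicidal behavior:** "the subject who has at least one of each suicidal behavior 5 items and non-suicidal self-injurious behavior item will be counted once". Its second sentence deals with repeated reports of suicidal behavior with non-suicidal self-injury (NSSI) and says that "the subject will be counted in the most severe suicidal behavior item".
- **Rule 3, ideation or behavior:** "the subjects who meets the criteria of (1) or (2) will be counted".
- **Rule 4, NSSI:** "In the treatment period the subjects who has non-suicidal self-injurious behavior item will be counted".

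Elsewhere NSSI stands outside suicidal behavior:

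- SAP 8.4.3.2 introduces its list with "The severe level of suicidal behavior 5 items from low to high" and then names preparatory acts, aborted attempt, interrupted attempt, actual attempt and suicidal behavior. NSSI is not among them.
- Protocol 12.7 classifies behavior from 0 (none) to 4 (actual attempt), with no category for NSSI.
- The form in protocol Appendix 3 describes NSSI as self-injury without suicidal intent and gives it a line of its own: "Has subject engaged in Non-Suicidal Self-Injurious Behavior".
- In the protocol's C-SSRS paragraph under Other Safety Analyses (17.3.5.4), "the number and percentage of subjects with suicidal ideation or suicidal behavior as recorded on the C-SSRS scale will be presented". NSSI is not mentioned there.

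SAP section 11, which records changes from the protocol, lists only the physical examination summary.

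**The concern.** Rule 2 is the definition behind the suicidal behavior count, and rule 3 refers back to it. If NSSI alone satisfies rule 2, a subject with no suicidal intent on record is reported as having suicidal behavior and, if there is also no ideation, is newly added to the combined count. Rule 4 already reports NSSI, so pooling it in rule 2 adds no information.

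The C-SSRS is one of the primary safety assessments. The study has a single arm and is evaluated descriptively, so the reported percentage is itself the result, and no comparator carries the same misclassification. Such events are likely to be few, so one or two reclassified subjects could be a large share of the count.

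**Working it through.** The documents give no figure on this point, and the sample size is not based on power, so there is nothing to reproduce. The check is logical, followed by simple arithmetic.

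**Step 1: how to read rule 2.** Rule 1 uses the same construction for the five ideation items, where it can only sensibly mean any one of them. Carried over, rule 2 means any of the five behavior items or NSSI.

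**Step 2: all combinations.** Let I = any ideation, B = any of the five behavior items, N = NSSI (1 = present).

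- Intended: behavior = B; combined = I or B.
- Natural reading: behavior = B or N; combined = I or B or N.
- Literal reading: behavior = B and N; combined = I or (B and N).

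| I | B | N | Behavior: intended / natural / literal | Combined: intended / natural / literal |
|---|---|---|---|---|
| 0 | 0 | 0 | 0 / 0 / 0 | 0 / 0 / 0 |
| 0 | 0 | 1 | 0 / **1** / 0 | 0 / **1** / 0 |
| 0 | 1 | 0 | 1 / 1 / **0** | 1 / 1 / **0** |
| 0 | 1 | 1 | 1 / 1 / 1 | 1 / 1 / 1 |
| 1 | 0 | 0 | 0 / 0 / 0 | 1 / 1 / 1 |
| 1 | 0 | 1 | 0 / **1** / 0 | 1 / 1 / 1 |
| 1 | 1 | 0 | 1 / 1 / **0** | 1 / 1 / 1 |
| 1 | 1 | 1 | 1 / 1 / 1 | 1 / 1 / 1 |

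On the natural reading, two combinations are added wrongly to the behavior count and one to the combined count. Both rates can only rise or stay the same, and the combined rate rises by no more than the behavior rate. On the literal reading, two combinations are lost from the behavior count and one from the combined count. Neither reading gives the intended count in every row.

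**Step 3: size.** With k wrongly added subjects and denominator n, the rate rises by k/n. The approximate enrollment is 140 (SAP 4.2). The smaller denominators and all values of k are assumptions.

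- n = 140: 1/140 = 0.71 points per subject. For k = 1 to 3 the rise is 0.71 to 2.14 points.
- n = 100: 1/100 = 1.00 point per subject.
- n = 60: 1/60 = 1.67 points per subject.

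If no subject had a behavior item and three had NSSI only, the behavior rate at n = 140 would read 3/140 = 2.1% instead of 0%. With two true cases and three with NSSI only it would read 5/140 = 3.6% instead of 2/140 = 1.4%. If k = 0, nothing changes.

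**Step 4: can the reader recover the right rate?** On the natural reading, the rule 2 count minus the rule 4 count is the number with B but not N. This falls short of the true behavior count by the number with both. Subtraction therefore works only if no subject has both.

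**Step 5: placement.** Rule 2 puts subjects in a most severe behavior item, but a subject with NSSI only has no level in the SAP 8.4.3.2 list. The rule does not say where that subject goes.

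**The case against.** The best defense is that rule 2 is badly worded rather than wrong in intent. Its second sentence can be taken partly as a de-duplication rule for subjects with both kinds of event. The severity list has no place for NSSI, and rule 4 suggests that NSSI was meant as its own category. This bears on intent but does not settle the count. Even if rule 2 is taken item by item, NSSI remains among the criteria of rule 2 that rule 3 picks up.

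The second defense is that the harm is contained. SAP 9.3.2 also calls for item-level frequencies, a most-severe distribution, a separate NSSI count and listings. No test or decision rule depends on the aggregate rows, and on the natural reading any error overstates a signal rather than hiding it. This stands as a limit on the harm. It does not repair the aggregate rows: subtraction fails where events overlap, and the most-severe distribution sums to the right total only if subjects with NSSI only are left out of it, which the rule does not say.

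Third, SAP section 2 states that its analysis details supersede the protocol's. A reader might infer that departing from the protocol's planned summary is an error in itself, but given that clause it is not. The firmer ground is that SAP 9.3.2 conflicts with the SAP's own list in 8.4.3.2.

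**Conclusion.** The point holds: rule 2 is wrong as written, and rule 3 inherits the fault. On the most natural reading, a subject with NSSI and no behavior item is counted as having suicidal behavior, and one who also has no ideation is added to the combined count. The size is about 0.7 percentage points per such subject at n = 140, and more with a smaller denominator.

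A reader might go further and infer that the reported rates will be inflated, or that every subject with NSSI raises both rates. The documents support neither. They give no NSSI frequency, so the effect may be zero. A subject with NSSI and a behavior item changes neither rate, and one with NSSI and ideation but no behavior item changes only the behavior rate. The direction also depends on the reading, since a literal one would undercount. This is worth correcting because it touches a primary safety assessment, but it affects two descriptive aggregate rows and no inference.

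**What to change.** Rewrite rule 2 along these lines: *a subject with at least one of the five suicidal behavior items during the treatment period will be counted once, in the most severe item*. Remove NSSI from both of its sentences. Deleting those words alone is not enough, because the at-least-one-of-each phrasing would remain, so replace that as well. Rule 3 then needs no change, and NSSI is reported under rule 4 only.

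While the text is open, confirm the severity order in SAP 8.4.3.2. It ranks a general suicidal behavior item above actual attempt, whereas the protocol 12.7 scale ends at actual attempt and the Appendix 3 form asks the general item as a yes/no presence question. This affects where a subject is placed, not whether NSSI is counted.

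The cost is a short SAP edit and the matching line of programming, with no new data.
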